13.5.5.2 Subject Recovery

The proportion of subjects to recover, defined as return to room air or baseline oxygen requirements, or discharged alive from the hospital, through day 28, will be summarized using descriptive statistics (totals and percentages) for subjects overall and by treatment group. The estimand of the proportion of recovery/discharge will be calculated by treatment group, along with 95% confidence intervals. A chi-square test will be used to test the significance in the proportion of subjects who recovered between the INOpulse and placebo treatment groups.

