⁶Local lab tests to be done prior to start of study drug and at End of Treatment. Labs include CBC w/differential, chemistry panel (sodium, potassium, chloride, CO₂, BUN, creatinine, glucose), LFTs (AST/ALT and total bilirubin), troponin (High Sensitivity Cardiac Troponin [HS-cTN]), D-dimer, NT-pro-BNP (if NT-pro-BNP is not available locally, BNP can be drawn and converted using the online calculator: <https://www.cardio.med.tohoku.ac.jp/calc/nt-probnp.html>), LDH, fibrinogen, ferritin, triglycerides, pro-calcitonin. If available at the local lab, also include CRP, Von Willebrands Factor, Factor VIII Activity, Protein C, Protein S, Homocysteine, Antithrombin 3, Thrombelastography (TEG), G6PD deficiency and Prothrombin gene G2021A. Lab results obtained within the previous 48 hours of randomization are acceptable for screening purposes if there has not been a significant change in the subject's clinical status.

⁷Upon initiation of treatment, SpO₂ should be monitored to ensure levels are >89%. During INOpulse therapy, SpO₂ should be monitored twice daily to ensure levels are > 80%. In the event an increase in O₂ flow rate is clinically indicated, SpO₂ should be monitored every 6 hours until stabilized. Oxygen flow requirements should be documented throughout the study.

⁸Symptoms of pulmonary rebound include hypoxemia, bradycardia, tachycardia, systemic hypotension, shortness of breath, near-syncope and syncope. If signs or symptoms of rebound are observed, the INOpulse should be restarted and the Investigator should contact the Sponsor. SpO₂, BP and vital signs should be measured every 30 minutes for 1 hour.

⁹All prior and concomitant medications, including all over-the-counter medications and all current COVID-19 treatments (all therapies prescribed for the treatment of COVID-19

¹⁰Medical history to include the reason for hospital admission.

*Complete Hospital Discharge Assessments only if it occurs before the End of Study. Otherwise, if the subject is still in hospital at the time of End of Study (30 day follow up post INOpulse completion), complete only the End of Study assessments indicated.

**Subjects will be assessed via telephone if discharged from the hospital. The assessments are to be performed in person, in the unlikely event the subject is still hospitalized.

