10.1.2. Medical History

At Screening, relevant medical history and demographics (sex, race, and ethnicity) will be assessed. Medical history is to include the reason for hospital admission.

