10.1.8. Respiratory Failure Status

Respiratory failure is defined as one of:

- Endotracheal intubation and mechanical ventilation
- Extracorporeal membrane oxygenation
- High-flow nasal cannula oxygen delivery (i.e., reinforced nasal cannula delivering heated, humidified oxygen with fraction of delivered oxygen ≥ 0.5 and flow rates of ≥ 30 l/min)
- Noninvasive positive pressure ventilation
- Clinical diagnosis of respiratory failure with initiation of none of these measures only when clinical decision-making is driven solely by resource limitation or in the event the subject is not intubated due to do not intubate (DNI) or do not resuscitate (DNR) status

10.1.9. 12-Lead Electrocardiogram (ECG)

12-Lead ECGs will be obtained and read locally after the subject has rested in a supine position for at least 5 minutes. Date, time, heart rate, and ECG interpretation will be recorded.

10.1.10. 8-point NIAID Ordinal Scale

The ordinal scale is an assessment of the subject's clinical status. The subject's clinical status should be assessed as described in **Table 2** and documented in medical records. Assessments should be performed every morning when subjects are hospitalized and via phone if discharged from the hospital as detailed in **Table 2**.

The 8-point NIAID Ordinal Scale is provided on the following page.

The scale is as follows:

Score	Outcome
1	Death
2	Hospitalized, requiring mechanical ventilation or ECMO
3	Hospitalized, requiring non-invasive ventilation or high flow oxygen
4	Hospitalized, requiring supplemental oxygen
5	Hospitalized, not requiring supplemental oxygen - requiring ongoing medical care (COVID-19 related or otherwise)
6	Hospitalized, not requiring supplemental oxygen - not requiring ongoing medical care (COVID-19 related or otherwise)
7	Not hospitalized - limitation on activities and/or requiring home oxygen
8	Not hospitalized, no limitations on activities

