9.0 Study Endpoints

Objectives	Endpoints
Primary	Primary endpoint

 The primary objective in this study is to verify the efficacy of INOpulse in subjects with COVID-19. 	
 Proportion of subjects who died or had respiratory failure (DRF as defined in Section 10.0 below) through Day 28.
	Secondary Endpoints
	
 8-point NIAID ordinal scale (Table 2 below) assessed at Day 7, 14, 28 and day of discharge. Proportion of subjects to recover, defined as return to room air or baseline oxygen requirements, or discharged alive from hospital [Through Day 28]. Proportion of subjects discharged alive from hospital [Through Day 28] Duration of hospitalization [Through Day 28]. Mortality [Through Day 28]: 
 All-cause mortality Cardiopulmonary mortality Proportion of subjects with a negative conversion of RT-PCR from a nasopharyngeal or bilateral nasal swab [through Day 28].
Secondary	
 The secondary objective in this study is to evaluate the safety of INOpulse in subjects with COVID-19.
	
 Proportion of subjects with adverse events leading to study drug discontinuation [Through Day 28].

Table 2: 8-Point NIAID Ordinal Scale

Score	Outcome
1	Death
2	Hospitalized, requiring mechanical ventilation or ECMO
3	Hospitalized, requiring non-invasive ventilation or high flow oxygen
4	Hospitalized, requiring supplemental oxygen
5	Hospitalized, not requiring supplemental oxygen - requiring ongoing medical care (COVID-19 related or otherwise)
6	Hospitalized, not requiring supplemental oxygen - not requiring ongoing medical care (COVID-19 related or otherwise)
7	Not hospitalized - limitation on activities and/or requiring home oxygen
8	Not hospitalized, no limitations on activities

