10.0 Conventions and Derivations

The primary endpoint is the proportion of subjects who died or had respiratory failure (DRF) through day 28 (treatment day 27), where respiratory failure is defined as one of the following:

- Endotracheal intubation and mechanical ventilation;
- Extracorporeal membrane oxygenation;
- High-flow nasal cannula oxygen delivery (i.e., reinforced nasal cannula delivering heated, humidified oxygen with fraction of delivered oxygen ≥ 0.5 and flow rates of ≥ 30 l/min);
- Noninvasive positive pressure ventilation;
- Clinical diagnosis of respiratory failure with initiation of none of these measures only when clinical decision-making is driven solely by resource limitation or in the event the subject is not intubated due to do not intubate (DNI) or do not resuscitate (DNR) status.

Duration of therapy will be calculated as the date of first dose of study drug on the INOpulse Usage Form through the date of last dose of study drug on the End of Treatment CRF page.

Baseline is defined as the last assessment prior to the first dose of study drug.

Body Mass Index is defined as subject weight (kg) divided by height (m²).

The age at COVID-19 diagnosis is defined as the number of years from the date of birth to the date of diagnosis of COVID-19, which will be derived based on the table below. No imputation will be done for missing disease diagnosis date (Year, Month, Day). The age calculation will be truncated to a whole number.

Table 3: Calculation for Age at COVID-19 Diagnosis

Observed Portion	Missing Portion	Formula to Calculate Duration
Year, Month, Day		(Date of Diagnosis – Date of Birth + 1)/365.25
Year, Month	Day	[Year (Date of Diagnosis) – Year (Date of Birth)] + [Month (Date of Diagnosis) – Month (Date of Birth)]/12
Year	Month, Day	[Year (Date of Diagnosis) – Year (Date of Birth)]

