13.5.2 Type I Error Rate

A gatekeeping methodology will be utilized for the primary and secondary hypothesis testing.² This gatekeeping method controls the study-wise Type I error rate at 5% associated with the study's primary and secondary endpoint families. If the primary endpoint is found to be statistically significant, the p-value of 5% will be used to test the first of the secondary endpoints. This testing of the secondary endpoints will continue in a hierarchical manner, until one of the statistical tests is not found to be significant. If this occurs, none of the remaining secondary endpoints will be tested. The hierarchy for the secondary endpoints is shown as they are listed in Section 13.5.5. If the primary endpoint is found not to be statistically significant, then the statistical testing of the secondary endpoint family will not be performed.

2. <https://www.fda.gov/regulatory-information/search-fda-guidance-documents/multiple-endpoints-clinical-trials-guidance-industry>

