13.5.4 Statistical Modeling of Primary Estimand

A logistic regression model will be utilized (which will allow us to adjust for covariates) to model the outcome of the proportion of subjects who experience respiratory failure or death through day 28. The outcome variable of respiratory failure (response) will be binary (yes/no). Factors in the model will be: treatment, baseline oxygen level (as a continuous covariate), number of co-morbidities (as a discrete numeric covariate), and age (as a continuous covariate). The estimand of the effect of treatment on the likelihood of respiratory failure will be calculated as an odds ratios with a 95% confidence interval, adjusted for age, baseline oxygen level, and number of co-morbidities. A difference in proportions will also be provided as part of the overall analysis along with a 95% confidence interval (Refer Appendix 4).

Example SAS code for the logistic regression model is as follows:

```
proc logistic;
  class treatment no_comorbidities;
  model response = age baseline_oxygen_level no_comorbidities treatment;
  run;
```

Baseline NIAID score will not be adjusted for, as all patients in this trial will have ordinal scale score of 4 (hospitalized requiring oxygen) at the time of trial entry, and the baseline disease severity will already be captured to a large extent by the oxygen level requirements.

As a sensitivity analysis, the primary analysis of DRF described in Section 12 above will be repeated on the PPAS.

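### Recovery counts a return to baseline oxygen, but the only baseline defined is the last pre-dose assessment; as written, worsening and coming back to entry oxygen in hospital is a recovery, while staying stable is not

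*SAP*

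**What the plan says.** SAP 13.5.5.2 gives three routes to recovery, any one of which suffices: "defined as return to room air or baseline oxygen requirements, or discharged alive from the hospital, through day 28". SAP 9.0 has the same rule ("Proportion of subjects to recover, defined as return to room air or baseline oxygen requirements, or discharged alive from hospital"), as do Protocol 7.2 and the synopsis. None of the four places explains what the baseline oxygen requirement is.

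SAP 10.0 defines the term for the whole plan: "Baseline is defined as the last assessment prior to the first dose of study drug". On status at that moment, SAP 13.5.4 says that "all patients in this trial will have ordinal scale score of 4 (hospitalized requiring oxygen) at the time of trial entry".

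Recovery is compared between arms by a chi-square test. It is second in the secondary hierarchy, after the NIAID score. Once a test in that hierarchy fails, SAP 13.5.2 stops the sequence: "If this occurs, none of the remaining secondary endpoints will be tested".

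**The concern.** A recovery endpoint should separate subjects who got better from those who did not. If the plan's own definition of baseline is put into the second route, the reference level is the oxygen the subject needed while acutely ill at enrolment. Getting back to that level after a deterioration is then a success, although the subject is no better than at entry and is still in hospital on oxygen. The same subject can be a failure on the primary endpoint and a success on recovery.

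Recovery also acts as a gate. If death or respiratory failure (DRF) and NIAID are both significant, the recovery test decides whether discharge, hospital duration, mortality and RT-PCR conversion are formally tested. A classification rule in that position should be fixed before unblinding.

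**Working it through.** **Step 1: which baseline applies.** Three things point to the entry value.
- SAP 10.0 is the only definition of baseline. The SAP 13.0 fallback for missing laboratory and vital-sign baselines is a screening value, also taken during the acute illness.
- The SAP uses baseline oxygen for the entry level in its models (13.5.4 and 13.5.5.1) and in the planned table of recovery by baseline oxygen level (Appendix 4). Protocol Table 2 labels Day 0 as baseline.
- No passage names pre-illness or home oxygen as the reference. Protocol 10.1.2 asks for relevant history and adds that "Medical history is to include the reason for hospital admission", but names no item for prior oxygen use.

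**Step 2: apply the rule.** Take three subjects, all on oxygen at entry, all still in hospital at Day 28, none ever on room air.

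| Course | Reading as written |
|---|---|
| Stays at entry flow | Not recovered: never left entry flow, so cannot return to it |
| Rises above entry flow, comes back | Recovered |
| Has a DRF event, later back at entry flow | Recovered, and a primary-endpoint event |

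The stable subject scores worse than the two who deteriorated.

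**Step 3: who is affected.** The clause changes a subject's result only if all four conditions hold: no room air by Day 28, no live discharge by Day 28, a rise above entry flow, and a return to it.

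**Step 4: size, by illustration.** The documents give no recovery rate or power for this endpoint, so there is no figure to reproduce. Assumptions: true recovery p of 80% on placebo and 90% on active; 250 per arm (500 subjects, 1:1, SAP 8.1); f is the share of truly non-recovered subjects who are counted as recovered.

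Observed rate = p + f(1 − p). With equal f, the difference becomes (1 − f) × 10 points.

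Power (two-sided 0.05) = Φ[(d − 1.96·se0)/se1], where se0 = √(2·p̄(1 − p̄)/250), p̄ is the mean of the two rates, and se1 = √((p1(1 − p1) + p2(1 − p2))/250).

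- f = 0: d = 0.10, se0 = √(2 × 0.85 × 0.15/250) = 0.0319, se1 = √((0.16 + 0.09)/250) = 0.0316. Power 88%.
- f = 10% in both arms: 0.80 + 0.10 × 0.20 = 0.82 and 0.90 + 0.10 × 0.10 = 0.91, so d = 0.09, se0 = 0.0306, se1 = 0.0303. Power 84%.

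| f placebo / f active | Observed rates | Difference | Power |
|---|---|---|---|
| 0 / 0 | 80.0% / 90.0% | 10.0 points | 88% |
| 5% / 5% | 81.0% / 90.5% | 9.5 points | 86% |
| 10% / 10% | 82.0% / 91.0% | 9.0 points | 84% |
| 10% / 0 (extreme) | 82.0% / 90.0% | 8.0 points | 73% |
| 0 / 10% (extreme) | 80.0% / 91.0% | 11.0 points | 94% |

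In subjects, 10% is 5 of the 50 non-recovered on placebo and 2 to 3 of the 25 on active. Starting from 75% versus 85% instead, power falls from 80% to 77% (f = 5%) or 75% (f = 10%).

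**The case against.** The strongest reply is that the harmful reading is not the natural one. The definition puts baseline oxygen beside room air under a single verb of return, so the likely sense is the subject's usual oxygen before the illness, for those who could never reach room air. That is probably the intent, and nothing shows that the authors meant entry oxygen. But the plan defines baseline once, uses baseline oxygen for the entry level, and names no collected item for the other meaning. A programmer following the text would arrive at entry oxygen.

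The group is also narrow, as Step 3 shows. The DRF example is hard to build from scheduled data: treatment stops at protocol-defined respiratory failure, and Table 2 schedules no oxygen flow in hospital after End of Treatment. Footnote 7 nevertheless says "Oxygen flow requirements should be documented throughout the study", so this limits the example without removing it.

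A reader might infer that subjects who never leave entry flow are unclassified, or that every subject qualifies from the start. The documents support neither: recovery needs a return, and a subject who never left has not returned. A reader might also take 73% or 94% as the likely power. Those figures need miscounting in one arm only, for which a double-blind trial offers no evident mechanism.

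**Conclusion.** The point stands as a definition that, applied as written, classifies some subjects wrongly in a gatekept secondary endpoint and can rank a worse course above a stable one. It should be fixed, but its reach is limited. The affected group is probably small, the primary endpoint is unaffected, and recovery is tested only if DRF and NIAID are both significant.

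Under the assumed 80% versus 90% recovery, equal miscounting of 5% to 10% of non-recovered subjects costs about 2 to 4 points of power; the one-arm results are outer bounds. The recovery rates and f are assumptions, and the direction of any distortion is not known in advance. That the wording misclassifies does not depend on them; it rests on the text alone.

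**What to change.** Before unblinding, amend SAP 9.0 and 13.5.5.2, Protocol 7.2 and the synopsis to say that the SAP 10.0 baseline does not apply to this endpoint. Define recovery through Day 28 as any of:
- no longer requiring supplemental oxygen (NIAID score 5 or higher);
- for a subject with documented home oxygen before COVID-19, return to that requirement;
- discharge alive.

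Add that a subject who dies by Day 28 is not counted as recovered, and state how relapse after recovery is counted. Without these rules, a subject who reaches room air and then dies within the window would still count.

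The cost is wording: an SAP amendment by the route in SAP 6.0 and a protocol clarification. For NIAID, Protocol 10.1.10 already says "Assessments should be performed every morning when subjects are hospitalized", and Table 2 schedules the score in hospital both on and off INOpulse. The first route therefore needs no new data and does not depend on oxygen flow after End of Treatment. The small downside is a site query for the few subjects on prior home oxygen, because that is not a named history item.

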17. STATISTICAL CONSIDERATIONS

This section provides a general description of the statistical methods to be used in analyzing both safety and efficacy data. The key statistical issues or considerations will be addressed. A more detailed statistical analysis plan will be provided in a separate document that will be finalized before unblinding of treatment assignment.

17.1. Primary Efficacy Analysis:

The primary analysis will be analyzed using a logistic regression model (Agresti, 2007, John Wiley and Sons) with treatment, age, gender and baseline stratification factors (used for stratified randomization) as covariates. Supportive analysis may be carried out while including other baseline subject level and site level covariates as needed (to be specified in the SAP).

The primary analysis is conducted at Day 28, however, we plan to conduct sensitivity analysis at Day 7 and Day 14 and day of discharge.

In addition, where appropriate, we plan to conduct time to event analysis to supplement the proportional analyses.

Details around the analysis plan will be provided in the SAP.

Expected Sample-Size

Initial assessment of the sample size is based on the historical experience of ~30% of hospitalized COVID-19 subjects deteriorating to needing increased respiratory support and the experience in our Emergency Expanded Access that indicates ~15% deteriorate.

Using 30% for the placebo arm and 15% for the iNO arm results in a sample size of 382 for a 1:1 randomized trial with 90% power for one-sided p-value of 0.025.

Based on this analysis, we are targeting a sample size of ~500 subjects. However, we note that the sample size may need to be re-assessed as the data on COVID-19 is rapidly evolving.

17.2. Interim Analysis:

An interim analysis for futility is planned after ~100 subjects have completed assessments through Day 28 in order to assess the failure rate in the iNO group versus placebo for the primary endpoint (death and respiratory failure). The interim analysis will be carried out by an independent external DMC based on pre specified criteria and stopping rules as detailed in the SAP.

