8.2 Randomization and Stratification

Subjects will receive placebo or iNO125 mcg/kg IBW/hr for 24 hours daily until resolution of hypoxemia, protocol defined respiratory failure, hospital discharge or Day 28, whichever occurs first. Randomization will be stratified based on the following four [2-level] factors in Table 1 below:

Table 1: Stratification Factors

Factor	Low	High
Oxygen Use	≤5 L/min	>5 L/min
NT-proBNP	<320 pg/ml	≥320 pg/ml
# of Comorbidities	0 or 1	≥2
Remdesivir use	No	Yes

The four comorbidities considered are

1. Diabetes;
2. Hypertension;
3. Cardiovascular disease (including ischemic heart disease, heart failure, cerebrovascular disease, peripheral vascular disease);
4. Obesity (BMI ≥ 30).

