13.5.5.3 Subject Hospital Discharge

The proportion of subjects to be discharged alive from the hospital, through day 28, will be summarized using descriptive statistics (totals and percentages) for subjects overall and by treatment group. The estimand of the proportion of hospital discharge will be calculated by treatment group, along with 95% confidence intervals. A chi-square test will be used to test the significance in the proportion of subjects who are discharged between the INOpulse and placebo treatment groups.

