13.5.5.5 Mortality

All-cause mortality will be defined as death from any cause through day 28 (treatment day 27). The all-cause mortality will be summarized using proportions, with all subjects in the ARAS included in the denominator.

Disease-specific mortality will be defined as death due to cardiopulmonary causes through day 28 (treatment day 27). This will be defined as having an adverse event under the respiratory body system/SOC, with outcome of death. It will be summarized using proportions, but the denominator will be the FES, excluding [subjects with] other causes of death through day 28.

Mortality rates will be displayed overall and by treatment group, age group, and gender as a subgroup analysis. The estimand of the proportion of mortality will be calculated by treatment group, along with 95% confidence intervals. A chi-square test will be used to test the significance in the proportion of mortality between the iNO and placebo treatment groups.

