13.5.5.6 RT-PCR Conversion

Confirmation of COVID-19 diagnosis will be done through RT-PCR testing. Samples will be taken at baseline and End of Treatment/discharge. RT-PCR results will be summarized as positive or negative using proportions, overall and by treatment group; this will be done in the ARAS dataset, which by definition requires positive at baseline. Among subjects who had a positive RT-PCR test at study enrollment, the test positivity rate at hospital discharge will be calculated by treatment group, along with 95% confidence intervals. A chi-square test will be used to test the significance in the proportion of positivity between the INOpulse and placebo treatment groups at discharge. Death will be imputed as a positive conversion even in the case the subject was a negative conversion and died.

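### Recovery, discharge, mortality and RT-PCR are tested with an unadjusted chi-square after stratified randomisation: valid, but slightly inefficient if the stratification factors are prognostic

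*SAP*

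**What the plan says.** On randomisation, SAP 8.2 states: "Randomization will be stratified based on the following four [2-level] factors in Table 1 below". The factors are oxygen use (up to or above 5 L/min), NT-proBNP (below or from 320 pg/ml), number of comorbidities (0 or 1, or at least 2) and remdesivir use.

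Four secondary endpoints are then tested as follows:

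- SAP 13.5.5.2, recovery: "A chi-square test will be used to test the significance in the proportion of subjects who recovered"
- SAP 13.5.5.3, discharge: "A chi-square test will be used to test the significance in the proportion of subjects who are discharged"
- SAP 13.5.5.5, mortality: "A chi-square test will be used to test the significance in the proportion of mortality". All-cause and cardiopulmonary mortality are separate components, so there are five tests in all.
- SAP 13.5.5.6, RT-PCR: "A chi-square test will be used to test the significance in the proportion of positivity"

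None of these sections mentions strata or covariates. The table list in SAP Appendix 4 holds no stratified or adjusted comparison for these endpoints, only subgroup summaries.

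The tests count toward error control. SAP 13.5.2 says: "This gatekeeping method controls the study-wise Type I error rate at 5% associated with the study's primary and secondary endpoint families", and on the order: "The hierarchy for the secondary endpoints is shown as they are listed in Section 13.5.5". Testing stops at the first non-significant result.

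**The concern.** Stratified randomisation balances the arms on the chosen factors. If those factors predict outcome, the difference between arms varies less from trial to trial than under simple randomisation. A plain chi-square does not use that reduction, so it tends to reject slightly too seldom.

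The SAP itself treats two of the four factors as prognostic. Sections 13.5 and 13.5.5 present oxygen and comorbidities as baseline severity, and 13.5.4 says that oxygen requirement captures most of it. The models for the primary endpoint (death or respiratory failure, DRF) and for the NIAID score (13.5.4, 13.5.5.1) adjust for oxygen level, comorbidities and age. The binary secondary endpoints drop all adjustment, and no reason is given. For NT-proBNP and remdesivir the documents say nothing about prognostic strength.

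What is at stake is a little power in a fixed sequence. The order is DRF, NIAID score, recovery, discharge, hospital duration, mortality, RT-PCR. A narrow miss at recovery would end formal testing of everything after it.

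**Working it through.** **Inputs.** From SAP 8.1, 8.2 and 13.5.2: 500 subjects, 1:1, two-sided 5%, four two-level factors. That makes 2⁴ = 16 cells, averaging 500/16 ≈ 31 subjects. Block size, factor prevalences, prognostic odds ratios and secondary event rates are not in the documents and are assumed.

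**The plan's own figure.** No rate or power is given for any secondary endpoint. The only power figure is 93% for DRF at 15% vs 6%. With 250 per arm and pooled rate 0.105:

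- SE under the null = √(2 × 0.105 × 0.895/250) = 0.0274
- SE under the alternative = √((0.15 × 0.85 + 0.06 × 0.94)/250) = 0.0271
- Power = Φ((0.09 − 1.96 × 0.0274)/0.0271) = 90.9%

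Other standard formulas give 88.9% (Wald, log odds) to 91.9% (arcsine), so 93% is approached but not matched. Nothing below depends on it. The odds ratio does reproduce: (0.06/0.94)/(0.15/0.85) = 0.362, with logarithm −1.017.

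**Why the chi-square is conservative.** Let R² be the share of outcome variance that lies between strata: R² = Σ wₛ(pₛ − p)²/[p(1 − p)]. Under stratified randomisation and no treatment effect, the variance of the difference is about (1 − R²) times what the chi-square assumes. The actual type I error is then about 2Φ(−1.96/√(1 − R²)):

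- R² = 0.026: 1.96/√0.974 = 1.986, error 4.7%
- R² = 0.082: 1.96/√0.918 = 2.046, error 4.1%
- R² = 0.180: 1.96/√0.820 = 2.164, error 3.0%

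**Simulation A.** Stratified permuted blocks of 4, prevalences 30/40/45/60%, chi-square vs CMH on 16 cells, 100,000 replicates or more for type I error and 50,000 for power. Treatment odds ratio 0.5 at a 15% control rate and 0.53 at 30%. Gains are taken before rounding.

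| Control rate | Factor odds ratios | R² | Type I error, chi-square / CMH | Power, chi-square / CMH | Gain (points) |
|---|---|---|---|---|---|
| 15% | all 1 | 0 | 5.0% / 5.0% | 68.0% / 68.1% | 0.1 |
| 15% | all 1.3 | 0.008 | 4.9% / 5.0% | 67.3% / 67.6% | 0.3 |
| 15% | 2, 1.5, 1.5, 1.2 | 0.026 | 4.7% / 5.0% | 66.7% / 67.5% | 0.9 |
| 15% | all 2 | 0.057 | 4.3% / 4.9% | 64.8% / 66.6% | 1.8 |
| 15% | 3, 2.5, 2, 1.5 | 0.082 | 4.1% / 5.0% | 62.9% / 65.8% | 2.9 |
| 15% | all 3 | 0.133 | 3.5% / 4.9% | 58.8% / 63.7% | 4.8 |
| 30% | 2, 1.5, 1.5, 1.2 | 0.040 | 4.6% / 5.0% | 83.4% / 84.2% | 0.8 |
| 30% | 3, 2.5, 2, 1.5 | 0.115 | 3.7% / 4.9% | 79.1% / 82.2% | 3.0 |
| 30% | all 3 | 0.180 | 3.0% / 4.9% | 73.9% / 79.5% | 5.6 |

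The simulated errors agree with the formula.

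**Simulation B.** Overall event rates fixed at 25% vs 15%, prevalences 30/40/50/50%, blocks of 4, 20,000 replicates. Power, chi-square vs CMH:

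- no prognostic effect: 81.0% vs 80.9%
- all 1.5: 80.4% vs 81.0%
- all 2: 80.7% vs 82.6%
- all 3: 82.2% vs 86.3%

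**Rare outcome.** At a 5% control rate and treatment odds ratio 0.4, power is 42.7% vs 42.9% for the moderate factors (2, 1.5, 1.5, 1.2) and 41.7% vs 42.7% for the strong ones (3, 2.5, 2, 1.5). At 6% vs 2%, the gain is 0.1 points with all odds ratios 1.5, 0.4 with all 2, and 1.9 with all 3.

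**The case against.** The strongest reply is that a prespecified unadjusted test is a legitimate choice. It is simple, it matches the proportion-by-arm estimands, and in no scenario did it exceed 5%. The protocol does not require more: section 17.1 names "treatment, age, gender and baseline stratification factors (used for stratified randomization) as covariates" for the primary analysis only and sets no test for the secondary endpoints. The gain depends on prognostic strength that the documents do not report. Its top end needs an odds ratio of 3 on every factor, an 81-fold range of odds (3⁴) between best and worst strata. Stratifying also has a price. With prevalences of 30/40/50/50%, the smallest cell holds about 500 × 0.3 × 0.4 × 0.5 × 0.5 = 15 subjects. At 5% mortality, about 4 to 5 of the 16 cells contained no death in simulation.

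Most of this stands, and it keeps the point small. It does not remove it: the SAP already relies on oxygen and comorbidities as severity measures, and stratifying on factors that turn out not to matter costs essentially nothing (80.9% vs 81.0%).

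A reader might infer that these tests are invalid, or that several points of power are lost at every step and so shut off the rest of the hierarchy. The documents support neither. The departure from 5% is in the conservative direction, the loss at the mortality step is close to nil, and recovery is reached only if DRF and the NIAID model are both significant.

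**Conclusion.** This is a cheap efficiency improvement, not a validity error. If the stratification factors are prognostic, the chi-square runs at about 4 to 5% instead of 5% for weak to strong factors (3.7% for the strong set at a 30% rate). The power given up is about 0.5 to 2 points for a common outcome with odds ratios of 1.5 to 2 per factor, about 3 points for the strong set, and 4 to 6 points only with odds ratio 3 on all four. For death it is near zero unless the factors are very strong. With non-prognostic factors there is no loss.

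The direction rests on the stratified design and needs only that the factors be prognostic, which the SAP implies for two of the four. The sizes rest on the assumed block size, prevalences, odds ratios and event rates. They are losses at single steps; no combined loss over the hierarchy was calculated.

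**What to change.** In SAP 13.5.5.2, 13.5.5.3, 13.5.5.5 and 13.5.5.6, replace the chi-square with a CMH test stratified by the randomisation factors, and report the stratum-adjusted risk difference with a 95% CI. This keeps the proportion-based estimand, whereas a logistic model would move the target to a conditional odds ratio. It also supplies a between-arm estimate, which the text for recovery, discharge and mortality lacks.

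State in advance how sparse cells are pooled, for example by dropping remdesivir use first and NT-proBNP second. For both mortality components use fewer strata from the start, such as oxygen use and comorbidities only. For consistency, replace the Mann-Whitney test of hospital duration in 13.5.5.4 with a stratified rank test (van Elteren). Add the adjusted results to the matching tables in Appendix 4.

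The cost is an SAP amendment before unblinding and a few lines of code, with no new data or subjects. The one real burden is fixing the pooling rule beforehand, because 16 cells are thin for rare events.
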